7.2.2 Dose Modification Guidance

The dose modification sequence by starting dose is shown in Table 5. A patient is normally allowed to have dose reductions no more than twice, e.g. dose reductions from 300 mg QD to 250 mg QD and then 200 mg QD or from 400 mg QD to 300 mg QD and then 200 mg QD is allowed. However, if the investigator judges that a dose lower than 200 mg QD is required for safety reasons, and that the patient could still benefit from study drug treatment at such a lower dose, then the dose may be further lowered to 200 mg QD, 3 weeks on and 1 week off, during each subsequent 4-week cycle.

Table 5 Dose Modification Sequence by Starting Dose

Daily Starting Dose	300 mg	400 mg**
-1 Dose	250 mg	300 mg
-2 Dose	200 mg	200 mg
-3 Dose*	200 mg on reduced schedule*	200 mg on reduced schedule*
	Off study drug	Off study drug

*Dosing schedule 200 mg QD, 3 weeks on/1 week off, every 28-day cycle.

**No new patients will be enrolled at the 400 mg QD dose.

Dose reduction guidelines for hematologic and non-hematologic toxicities other than hypertension, proteinuria, liver function impairment and hemorrhage are shown in [Table 6](#). In principle, treatment should be held until AE/toxicity resolves or improves to \geq Grade 1. If a patient has a Grade 3 toxicity that is expected to be manageable and reversible with a dose reduction, treatment should be held until toxicity resolves to \leq Grade 1. Patients with Grade 3 non-haematologic toxicity that does not resolve to \leq Grade 1 within 3 weeks should permanently discontinue the study drug.

Table 6 Dose Modification for Hematologic and Non-Hematologic Toxicities

NCI CTCAE v4.03 Toxicity Grading	Action
Grade 1 or 2	None
Grade 3 or 4	
Expected manageable/reversible with dose reduction	Hold ^a
Toxicity remains Grade 3 >7 days	Discontinue treatment
Toxicity lasts ≤7 days and resolves to ≤Grade 1	Reduce 1 dose level
Reoccurrence of Grade 3 toxicity	Reduce 1 dose level or discontinue treatment ^a
Reoccurrence of Grade 4 toxicity	Discontinue treatment
Not expected manageable/irreversible with dose reduction	Discontinue treatment

^a Treatment should be withheld until toxicity recovers to ≤Grade 1. For patients who cannot recover within 21 days, the study drug should be discontinued permanently.

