7.2 Dose Modification

7.2.1 General Dose Adjustment Note

The severity of AEs will be graded according to the NCI CTCAE v. 4.03. Reasons for dose modifications or delays, the supportive measures taken, and the outcome will be documented in the patient's chart and recorded in the CRF.

- For any concomitant conditions already apparent at baseline, the dose modifications will apply according to the corresponding shift in toxicity grade, if

the investigator feels it is appropriate. For example, if a patient has Grade 1 asthenia at baseline that increases to Grade 2 during treatment, this will be considered a shift of one grade and treated as Grade 1 toxicity for dose-modification purposes.

- For toxicities that are considered by the investigator to be unlikely to develop into serious or life-threatening events, treatment will be continued at the same dose without reduction or interruption. In addition, no dose reductions or interruptions will be required for anaemia (non-haemolytic) because it can be satisfactorily managed.
- To recover from acute toxicity, unless otherwise indicated, the treatment can be delayed for up to 21 days. If a treatment delay longer than 21 days is required, the patient should be discontinued from the study drug. Continuation/resumption of surufatinib treatment after an interruption of more than 21 days must be discussed with the medical monitor or his or her designee.
- Where several toxicities with different grades or severity occur at the same time, the dose modifications should be according to the highest grade observed.

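### The general hold sentence in Protocol 7.2.2 prints ≥ Grade 1 where every other signed recovery threshold in Section 7.2 says ≤ Grade 1; one sign needs correcting

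*Protocol*

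**What the plan says.** Protocol 7.2.2 covers haematologic and non-haematologic toxicities other than hypertension, proteinuria, liver impairment and haemorrhage. Its general rule reads "In principle, treatment should be held until AE/toxicity resolves or improves to" ≥ Grade 1.

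The text around that sentence uses the opposite sign:

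- The next sentence, for a Grade 3 toxicity expected to be manageable, says "treatment should be held until toxicity resolves to" ≤ Grade 1.
- The sentence after it says that Grade 3 non-haematologic toxicity not back to ≤ "Grade 1 within 3 weeks should permanently discontinue the study drug".
- Table 6 footnote a, attached to the Hold action for Grade 3 or 4, says "Treatment should be withheld until toxicity recovers to ≤Grade 1" and then "For patients who cannot recover within 21 days, the study drug should be discontinued permanently".
- The Table 6 row for restarting one dose level lower applies when "Toxicity lasts ≤7 days and resolves to ≤Grade 1". The row directly above it stops treatment when "Toxicity remains Grade 3 >7 days".

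Protocol 7.2.1 sets the general time limit: "To recover from acute toxicity, unless otherwise indicated, the treatment can be delayed for up to 21 days". In Section 7.2.3, Tables 8, 9 and 10 state their recovery thresholds as ≤ Grade 1.

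**The concern.** The sign decides when a held patient may be dosed again. With ≤ Grade 1, the event must be almost gone. With ≥ Grade 1, an event that has improved but is still Grade 2, or even Grade 3 after Grade 4, would meet the sentence.

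The sentence is an operative instruction. Protocol 3.3 names Section 7.2.2 among the measures that protect patients, and Protocol 12.2 makes the sponsor responsible for clear and consistent protocols. At stake are patient safety and consistent dosing between sites. The statistics are not affected: no sample-size calculation, success rule or SAP derivation uses this threshold, and SAP Section 15 only describes dose reductions and interruptions after they have happened.

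**Working it through.** The plan gives no figure to reproduce here, so the check is a comparison of texts.

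**Step 1. Count the signed Grade 1 recovery thresholds in Protocol 7.2.**

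| Place | Sign | Count |
|---|---|---|
| 7.2.2, general hold sentence | ≥ | 1 |
| 7.2.2, next sentence (manageable Grade 3) | ≤ | 1 |
| 7.2.2, 3-week sentence (Grade 3 non-haematologic) | ≤ | 1 |
| Table 6, restart row | ≤ | 1 |
| Table 6, footnote a | ≤ | 1 |
| Table 8, Grade 2 hold row, Grade 3 row, footnote | ≤ | 3 |
| Table 9, Grade 2 and Grade 3 | ≤ | 2 |
| Table 10, Grade 2 | ≤ | 1 |

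The ≤ statements total 1 + 1 + 1 + 1 + 3 + 2 + 1 = 10, against one ≥ statement. Table 7 (hypertension) asks for Grade 1 or baseline without a sign and is not counted. After the correction the count would be 11 to 0.

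**Step 2. What the printed sentence would permit.** Under Table 6, Grades 1 and 2 need no action, so holds start at Grade 3 or 4. The sentence asks for resolution or improvement, so an end grade counts only if it is lower than the starting grade.

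| Grade at hold | Grade now | Improved? | Meets ≤ Grade 1 | Meets ≥ Grade 1 as printed |
|---|---|---|---|---|
| 3 | 3 | no | no | no |
| 3 | 2 | yes | no | **yes** |
| 3 | 1 | yes | yes | yes |
| 4 | 4 | no | no | no |
| 4 | 3 | yes | no | **yes** |
| 4 | 2 | yes | no | **yes** |
| 4 | 1 | yes | yes | yes |

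The two signs give different answers for three moves: 3 to 2, 4 to 3 and 4 to 2.

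**Step 3. Which text corrects each of these.**

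- *Grade 3 to 2:* the next sentence (for a manageable Grade 3 event) and footnote a both require ≤ Grade 1.
- *Grade 4 to 3 or 2:* the next sentence and the 3-week sentence are both limited to Grade 3. The restart row sits under the Grade 3 or 4 heading, but it sets the dose on restart and not the length of the hold. Footnote a is the only explicit correction of the hold rule.

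**Step 4. The Table 6 timing rows.** A first, manageable Grade 3 event can take six courses, defined by the day it leaves Grade 3 and the day it reaches ≤ Grade 1.

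| Leaves Grade 3 | Reaches ≤ Grade 1 | Restart row read with the row above | Restart row read alone |
|---|---|---|---|
| by day 7 | by day 7 | one level lower | one level lower |
| by day 7 | days 8–21 | one level lower | no stated dose |
| by day 7 | after day 21 | discontinue (footnote a) | discontinue (footnote a) |
| days 8–21 | days 8–21 | discontinue (7-day row) | discontinue (7-day row) |
| days 8–21 | after day 21 | discontinue | discontinue |
| after day 21 | after day 21 | discontinue | discontinue |

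Read with the row above, Table 6 settles 6 of 6 courses. Read alone, the restart row leaves 1 of 6 open. These are courses, not patients.

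**The case against.** The strongest reply is that nobody would be misled. The sentence states only a general principle, the next one gives the working rule for Grade 3, and footnote a sits on the Hold action itself. The sign may also come from reading the PDF: in Protocol 2.2.1 a concentration and a dose appear to have lost their micro prefix. Most of this stands. An early restart is unlikely, and the sign must be checked in the source. But the two ≤ signs that follow in the same paragraph came through correctly, which makes a misread less likely, and for Grade 4 events the correction rests on a footnote alone.

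A reader might also infer three stronger points. The documents support none of them.

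- *That an unchanged Grade 3 event already meets the sentence on the day the hold starts.* It does not. The sentence requires resolution or improvement, and an unchanged event shows neither.
- *That Table 6 leaves recovery on days 8 to 21 without a restart dose.* This follows only if the restart row is read in isolation. It is the natural complement of the row above, which concerns time spent at Grade 3, and read that way it leaves no gap. Reading it alone would also make the 21-day window in footnote a almost pointless for a first Grade 3 event.
- *That the 7-day stop conflicts with the 21-day limit.* The two work in sequence. Section 7.2.1 makes its 21-day allowance subject to other instructions, and the 7-day row is one.

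**Conclusion.** The general hold sentence is wrong as printed. It stands one against ten in Section 7.2, and read literally it would permit restart after partial improvement in three situations (Grade 3 to 2, Grade 4 to 3, Grade 4 to 2). The practical risk is small, because the surrounding text gives the right threshold. It is least well covered for Grade 4.

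This conclusion assumes that the source PDF carries the same sign. If it does not, the point falls away. The share of patients who could be affected is not given. This is a minor dosing-safety correction, and no statistical figure changes.

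**What to change.** Check the sign in the source PDF. If it is confirmed, change the threshold in the general hold sentence from ≥ Grade 1 to ≤ Grade 1. The cost is one character in a clarification letter or the next amendment, with no new visits, procedures or data.

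Rewording the timing rows of Table 6 is optional clarification only. If it is done, the new text should cover both grades, for example: *Still Grade 3 or higher after 7 days: discontinue. Below Grade 3 by day 7 and ≤ Grade 1 within 21 days: restart one dose level lower; otherwise discontinue.* Naming Grade 3 or higher matters, because a row that named Grade 3 alone would give no action for an event still at Grade 4 after day 7. No clause linking the 7-day and 21-day limits is needed.

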7.2.3 Dose Modification for Important Identified Risks

Dose modifications for important identified risks are provided in Table 7 (hypertension), [Table 8](#) (proteinuria), [Table 9](#) (liver function impairment), and [Table 10](#) (hemorrhage).

Table 7 Dose Modification for Hypertension

Grade and Definition	Dose Modification	Suggested Actions
Grade 1: prehypertension (systolic BP120-139 mmHg or diastolic BP 80-89 mmHg)	None.	None.
Grade 2: Stage 1 hypertension (systolic BP140-159 mmHg or diastolic BP 90-99 mmHg); medical intervention indicated; recurrent or persistent(≥24 hours); symptomatic increase by >20 mmHg (diastolic) or to >140/90 mmHg if previously within normal range; monotherapy indicated	None.	Treatment target: control blood pressure to below 140/90 mmHg. If patient has already received antihypertensive treatment at baseline, the dose should be increased or treatment changed. If patient did not receive treatment at baseline, monotherapy should be administered. Refer to relevant anti-hypertensive treatment guidelines for dose administration and modification and consult cardiologist if necessary.
Grade 3: Stage 2 hypertension (Systolic pressure ≥ 160mmHg or diastolic pressure ≥ 100mmHg); medical intervention indicated; more than one drug or more intensive therapy than previously used indicated	If BP >160/100mmHg lasts for >3 days after initiation of anti-hypertensive treatment or modification of current anti-hypertensive treatment, surufatinib treatment should be held. If hypertension resolves to Grade 1 or baseline level within 21 days, sulfatinib treatment could be re-started at a lower dose level.	Treatment target: control blood pressure below 140/90 mmHg. Initiate antihypertensive treatment, increase dose of current treatment, or add other treatments. For use and adjustment of antihypertensive treatment, refer to relevant treatment guidelines or consult cardiologist if necessary.

Table 7 Dose Modification for Hypertension

Grade and Definition	Dose Modification	Suggested Actions
Grade 4: Life-threatening consequences (e.g., malignant hypertension, transient or permanent neurologic deficit, hypertensive crisis); urgent intervention indicated	Discontinue surufatinib treatment.	Emergent medical intervention.

Table 8 Dose Modification for Proteinuria

Grade and Definition	Dose Modification	Suggested Actions
Grade 1: 1+ proteinuria; urinary protein <1.0 g/24 hours	None.	Follow up as planned schedule.
Grade 2: 2+ or 3+ proteinuria; urinary protein 1.0 - 2.0 g (excluding 2.0 g)/24 hours	None.	Provide supportive treatment and increase the frequency of urine monitor to once a week; consult nephrologist if necessary.
Grade 2: Proteinuria \geq 2+; urinary protein 2.0 - 3.5 g (excluding 3.5 g)/24 hours	Hold surufatinib treatment and resume treatment at the same dose level if proteinuria resolves to \leq Grade 1 within 21 days	Provide supportive treatment and increase the frequency of urine monitor to once a week; consult nephrologist if necessary.
Grade 3: Urinary protein \geq 3.5 g/24 hours	Hold surufatinib. If test results resolves to \leq Grade 1 within 21 days, resume at a lower dose.	Provide supportive treatment and increase the frequency of urine monitor to once or twice a week; consult nephrologist if necessary.

^a If urine dipstick reveals proteinuria 2+, 24-hour urine collection should be performed for determination of total protein within one week. The CTCAE grade recorded for proteinuria should be determined by the 24-hour urine collection, however the start date of the AE will be recorded as the first instant of proteinuria (i.e. urine dipstick). If surufatinib dose has been reduced to 200mg QD and a further dose reduction is required for recurrent proteinuria, keep the same daily dose of 200 mg QD of surufatinib for 3 consecutive weeks followed by 1-week drug holiday and repeat for each treatment cycle, (i.e. 3 weeks on and 1 week off; every 4 weeks constitutes a treatment cycle). If proteinuria cannot resolve to \leq Grade 1 after a dose interruption of 21 days, continuation/resumption of surufatinib treatment should be discussed with the medical monitor. Surufatinib treatment should be discontinued if a patient develops nephrotic syndrome.

Table 9 Dose Modification for Liver Function Impairment

Grade and Definitions	Dose Adjustment	Suggested Actions
Grade 1: ALT >1-3 \times ULN or AST >1-3 \times ULN	None.	Follow up per planned schedule. Check total bilirubin. ^a
Grade 2: ALT >3-5 \times ULN or AST >3-5 \times ULN	Maintain the original dose, provide supportive care of complications of liver impairment, observation for 1 week, If the ALT and AST is	Check total bilirubin. ^a Provide supportive care and increase the frequency of liver function monitor to 1-2 times a week.

Table 9 Dose Modification for Liver Function Impairment

Grade and Definitions	Dose Adjustment	Suggested Actions
	stable or declining, continue with the original dose treatment; If the ALT and/or AST continue to rise significantly, then interrupt surufatinib; resume treatment at a lower dose if transaminase elevation resolves to \leq Grade 1 within 21 days; otherwise discontinue treatment.	
Grade 3: ALT $>5 \times$ ULN or AST $>5 \times$ ULN	Hold surufatinib; resume treatment at the lower dose if resolves to \leq Grade 1 within 21 days; otherwise discontinue treatment.	Check total bilirubin. ^a Provide supportive care and increase the frequency of liver function monitor to twice a week; consult expert if necessary.
Grade 4: ALT $>20 \times$ ULN or AST $>20 \times$ ULN	Discontinue treatment.	Check total bilirubin. ^a Urgent medical intervention indicated.

^a If ALT or AST escalates to 3 times baseline level with bilirubin $>2 \times$ ULN, the biochemical criteria for Hy's Law have been met, surufatinib should be discontinued immediately, and the event should be reported to the sponsor within 24 hours. See [Appendix 7](#) for important additional information.

Table 10 Dose Modification for Hemorrhage

Grade and Definitions	Dose modification	Suggested Actions
Grade 1	None.	Follow up per planned schedule.
Grade 2	Hold surufatinib treatment; Resume at a lower dose if resolves to \leq Grade 1 within 21 days.	Active management.
Grade 3 or higher	Discontinue treatment.	Immediate medical intervention to identify and treat the source of bleeding.

7.3 Concomitant and Excluded Therapies

7.3.1 Concomitant Therapies

Concomitant therapy includes any prescription medications or over-the-counter preparations used by a patient between the 7 days preceding the screening evaluation and the termination visit.

- Patients who use hormonal therapy with GnRH agonists for prostate cancer, oral contraceptives, hormone-replacement therapy, or other allowed maintenance therapy should continue their use.
- Prophylactic use of anticoagulation for the maintenance of patency of permanent indwelling central venous access devices or for patients at high risk of venous thromboembolism is permitted during study treatment. If patients are receiving low-dose anti-coagulation at study entry:

- Patients who are receiving warfarin or Coumadin-like products should have their INR monitored and maintained at the lower end of the therapeutic range (ie, close to 2.0 if the therapeutic range is 2.0 – 3.0).
- Patients who require low-molecular-weight heparin should receive the prophylactic dose and monitoring as specified by the appropriate product information label.
- Patients who develop arterial thromboembolic events should discontinue the study drug. If a patient suffers a venous thromboembolic event whilst still receiving study drug, it may still be possible for him or her to remain on study drug under adequate monitoring and dose modification.
- Patients who have functioning pNETs or epNETs and have been on a stable dose of a somatostatin analogue (SSA) for a minimum of 2 months prior to the first dose of study drug for control of their secretory symptoms will be permitted to enroll in the dose expansion phase.
- All supportive measures consistent with optimal patient care will be given throughout the study.
- All concomitant medications should be reported to the investigator and recorded on the appropriate CRF.

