3.3 Benefit and Risk Assessment

Based on the available non-clinical and clinical data, identified risks of surufatinib include hepatic disorders, proteinuria, hypertension, myelosuppression, haemorrhage, and acute kidney injury. Potential risks include infection, intestinal obstruction, myocardial

ischaemia, cardiac failure, thromboembolism, pancreatitis, GI perforation, and posterior reversible encephalopathy syndrome. These are further described in the surufatinib IB.

Appropriate exclusion criteria, monitoring, and dose modification guidance are included in the protocol to ensure the safety of patients enrolled in the clinical trial. Patients are excluded if they have signs, symptoms, or history that may put them at risk in the context of the identified and potential risks of surufatinib including abnormal serum total bilirubin or ALT/AST or other signs of hepatic damage; urine protein $\geq 2+$; uncontrolled hypertension; abnormal neutrophil count, platelet count, or haemoglobin level; signs of risk of haemorrhage; creatinine clearance <60 mL/min; conditions that could possibly result in gastrointestinal tract hemorrhage or perforation; clinically significant cardiovascular disease; history of thromboembolic events; and posterior reversible encephalopathy syndrome (PRES). Patients with other disease, metabolic disorder, physical examination abnormality, abnormal laboratory result, or any other condition that investigators suspect may prohibit use of the investigational product, affect interpretation of study results, or put the patient at high risk are also excluded.

[Section 7.2.3](#) provides detailed guidance on dose modifications for important identified risks including hypertension, proteinuria, liver function and haemorrhage, and general dosing guidance to protect subjects are included in [Section 7.2.2](#). Thus, the identified and potential risks of treatment with surufatinib are appropriately mitigated by measures in the protocol.

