7.1.8 Important Potential Risks

The important potential risks of surufatinib include the following: infection, intestinal obstruction, gastrointestinal perforation, myocardial ischaemia, cardiac failure, venous thromboembolism, arterial thromboembolism, and pancreatitis. One patient in the 2015-012-00US1 trial experienced grade 3 PRES, which was deemed related to study drug and was considered resolved. For more information, please see surufatinib IB.

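### For arterial thromboembolic events, Section 7.3.1 says discontinue without qualification, while Table 6 would hold and then reduce the dose for some of them; nothing says which governs

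*Protocol*

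**What the plan says.** **Section 7.3.1, Concomitant Therapies.** Among the bullets on anticoagulation: "Patients who develop arterial thromboembolic events should discontinue the study drug". The next sentence deals with venous events occurring on treatment and says "it may still be possible for him or her to remain on study drug under adequate monitoring and dose modification".

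**Section 7.2.2, Dose Modification Guidance.** The scope of the general table is set by exception: "Dose reduction guidelines for hematologic and non-hematologic toxicities other than hypertension, proteinuria, liver function impairment and hemorrhage are shown in" Table 6. The four excepted toxicities have their own tables (7 to 10) in Section 7.2.3. None of those covers thromboembolism.

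**Table 6.** Grade 1 or 2 carries no action. For Grade 3 or 4, "Expected manageable/reversible with dose reduction" leads to a hold. Two rows then follow the course of the event: "Toxicity remains Grade 3 >7 days" leads to discontinuation, and "Toxicity lasts ≤7 days and resolves to ≤Grade 1" leads to a reduction of one dose level. A second Grade 3 episode allows either a reduction or discontinuation. A second Grade 4 episode, or a toxicity not expected to be manageable, means discontinuation.

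**Sections 7.1.8 and 3.3.** Section 7.1.8 includes "venous thromboembolism, arterial thromboembolism, and pancreatitis" in its list of important potential risks. Section 3.3 also names thromboembolism as a potential risk, sends the reader to 7.2.3 and 7.2.2 for dose guidance, and concludes: "Thus, the identified and potential risks of treatment with surufatinib are appropriately mitigated by measures in the protocol". It does not mention 7.3.1.

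**The concern.** A site managing an arterial event would naturally open Section 7.2, find that the event is not one of the four exceptions, and apply Table 6. The only instruction written for arterial events sits in a different section, among bullets about anticoagulant use. Two sites could each follow the protocol as written, and one would resume drug where the other stops it.

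The first thing at stake is consistent safety conduct for an event class that the protocol itself lists as an important potential risk. The second is how the event is reported. SAP Section 17.1.2 counts TEAEs leading to discontinuation from the recorded action of drug withdrawn, and Section 17.1.3 counts TEAEs leading to adjustment from interruption, reduction or increase. The same manageable Grade 3-4 arterial event would appear in the first table under 7.3.1 and in the second under Table 6. Duration of exposure and dose intensity (SAP Section 15) would differ as well.

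**Working it through.** No arithmetic applies. The check compares the 7.3.1 sentence with each Table 6 pathway, first for arterial and then for venous events.

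**Step 1: does Table 6 cover these events?** Its scope sentence excepts four toxicities by name. Thromboembolism is not one of them, and Tables 7 to 10 do not address it. On the plain wording, it does.

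**Step 2: arterial events.**

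| Course of the event | Section 7.3.1 | Table 6 | Result |
|---|---|---|---|
| Grade 1-2 | Discontinue | No action | Conflict, if such grades occur |
| Grade 3-4, manageable, resolved to Grade 1 or below within 7 days | Discontinue | Hold, then reduce one level | Conflict |
| Grade 3 for more than 7 days | Discontinue | Discontinue | Agree |
| Second Grade 3 episode | Discontinue | Reduce or discontinue | Both can be met by discontinuing |
| Second Grade 4 episode | Discontinue | Discontinue | Agree |
| Not manageable or irreversible | Discontinue | Discontinue | Agree |

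The first row is conditional. Whether an arterial event can be graded 1 or 2 depends on the CTCAE v4.03 term definitions, which the documents do not reproduce; Section 9.5 gives only the general scale. The second row does not depend on this.

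**Step 3: venous events.** The 7.3.1 sentence is permissive, and it makes staying on drug conditional on monitoring and dose modification. At Grade 1-2, Table 6 asks for no action, which is consistent with remaining on drug. At Grade 3-4, a site that holds, reduces or stops according to Table 6 breaches nothing in 7.3.1. There is no conflict.

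**Step 4: is there a tie-breaker?** The only priority rule in Section 7.2.1 concerns several toxicities of different grade at the same time. The early-discontinuation list in Section 5.6 has no arterial-event criterion. Neither 7.2.2 nor 7.3.1 refers to the other.

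**Step 5: to whom does the arterial sentence apply?** It follows a lead-in about patients on low-dose anticoagulation at study entry. In the text as extracted, the indentation is lost, so one cannot tell whether the bullet is nested under that lead-in. Nested, it would cover only those patients; otherwise it covers everyone.

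**The case against.** The strongest reply is that a specific rule displaces a general one. Table 6 is a residual table, introduced as guidelines, and the accompanying text says that holding applies in principle. The 7.3.1 sentence names one event type and one action. An experienced investigator would probably treat it as controlling. That is a natural reading and it lowers the severity. It does not remove the problem, because where this protocol wants a special rule to displace Table 6 it says so by naming the exception, and it does not name this one.

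A second reply is that the practical effect may be small. Recent thromboembolic events are an exclusion criterion (Section 6.2, criterion 12), many arterial events may be judged unmanageable and so stopped under both sections, and patients who stop for reasons other than progression continue tumor assessments (Section 5.5), which limits any effect on the PFS endpoints. All of this stands. The point concerns safety conduct, exposure and the discontinuation tables, not the primary analysis.

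A reader might also infer that the venous sentence contradicts Table 6, because Table 6 stops drug when Grade 3 lasts more than 7 days while 7.3.1 lets the patient continue. The documents do not support that: 7.3.1 says only that continuing may be possible, and it calls for dose modification in the same sentence.

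**Conclusion.** The protocol contradicts itself for a defined subset of arterial thromboembolic events: those at Grade 3-4 judged manageable that resolve to Grade 1 or below within 7 days, and those at Grade 1-2 if CTCAE allows such grades. A reader might go further and conclude that sites can never satisfy both sections. That is too broad, since three of the six arterial pathways in the comparison agree outright and a fourth can be handled in a way that meets both.

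The size in patients cannot be given, because the documents state no thromboembolic event rate. The conclusion rests on taking Table 6's scope sentence at its word and on the absence of any stated precedence. If the arterial bullet is nested under the low-dose anticoagulation lead-in, the conflict is confined to those patients, and all others are under Table 6 alone. This is a modest but real inconsistency that should be corrected.

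**What to change.** Reconcile the arterial sentence in Section 7.3.1 with the scope sentence of Section 7.2.2 and Table 6, so that one instruction applies to each arterial event, and cross-reference the two sections. If the 7.3.1 sentence is meant to govern, arterial events need to be named among the exceptions to Table 6; if Table 6 is meant to govern, the 7.3.1 sentence needs to say so. If the arterial sentence is not meant to be limited to patients on low-dose anticoagulation at entry, set it apart from that list. The venous sentence needs no change to remove a conflict, although a pointer to Section 7.2 would help. The choice of clinical rule is the sponsor's.

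The cost is one exception or footnote in Section 7.2.2 and a cross-reference in 7.3.1. No new data, analyses or patients are needed.
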